5.3. FULL ANALYSIS SET (FAS)

This set includes all subjects in the treated analysis set who provide at least one photosensitivity endpoint that was defined as primary or secondary and was not excluded due to an important protocol deviation relevant to the evaluation of photosensitivity. Descriptive and model based analyses of photosensitivity endpoints will be based on the FAS.

5.4. PHARMACOKINETIC SET (PKS)

The pharmacokinetic set includes all subjects who were randomized and treated with at least one dose of study drug BI 730357 and have at least one evaluable primary PK parameter, and are without important protocol deviations thought to have a relevant impact on the PK of BI730357. Whether a protocol deviation is relevant will be decided no later than in the report planning meeting.

6. GENERAL CONSIDERATIONS

Derivation of the PK parameters for BI 730357, in plasma, and generation of the PK analysis datasets, and statistical outputs (table, listing and figures), will be the responsibility of the sponsor. [REDACTED] biostatistics is only responsible for generating PK SDTM datasets PC and PP using the PK concentration and PK parameter data files received from the sponsor.

The summaries and data listings of all non-PK data as well as the statistical inferential analyses of the primary, secondary and further endpoints of photosensitivity variables will be the responsibility of the study biostatistician at [REDACTED]

Some minor modifications may be necessary to the planned design of tables, figures, and listings to accommodate data collected during the actual study conduct.

6.1. SUMMARY STATISTICS

For qualitative variables, the population size (N for sample size and n for available data) and the percentage (of available data) for each class of the variable will be presented. Quantitative variables will be summarized using descriptive statistics, including n, mean, standard deviation (SD), median, interquartile range (IQR calculated as third quartile [Q3] minus first quartile [Q1]), minimum, and maximum values. In addition, 10th percentile (P10), 90th percentile (P90), coefficient of variation (CV%), geometric mean (gMean) and geometric CV% (gCV%) will also be presented for PK concentration data and all PK parameters, where applicable.

Tabulations of frequencies for categorical data will include all possible categories and will display the number of observations in a category as well as the percentage (%) relative to the respective treatment

Document: L:\BIOS\Boehringer_Ingelheim_Pharmaceuticals\BI730357\1407-0037_MZA56588\Biostatistics\Documentation\SAP

Author: [REDACTED] Version Number: Final V2.0
Version Date: 23JUL2020

Template No: CS_TP_BS016 – Revision 5
Effective Date: 01Apr2018

Reference: CS_WI_BS005

group. The category missing will be displayed only if there are actually missing values.

6.2. TREATMENT SUMMARIZATION

In general, data will be presented for each treatment group (BI 730357 400 mg QD, Placebo QD, BI 730357 300 mg BID, Placebo BID and ciprofloxacin 500 mg BID). Data for subjects in the following combined treatment groups will also be presented when appropriate:

- All subjects combined, presented as Overall
- All BI 730357 treated subjects combined from the 2 dose groups, presented as BI 730357 Pooled
- All placebo treated subjects combined from the 2 dose groups, presented as Placebo Pooled

6.3. PRECISION

Non-PK variables (ie, primary, secondary, further endpoints and safety variables), including derivations thereof, will be reported to the same precision as the source data. Derived variables will be reported using the same precision to those from which they were derived. For the reporting of descriptive statistics, the minimum and maximum values will be presented to the same precision as the source data (base precision); base precision+1 for the mean, median and confidence intervals (CIs); and base precision+2 for the SD and IQR (see APPENDIX 1). Percentages will be presented with one decimal point.

6.4. REFERENCE START DATE AND STUDY DAY

Study Day will be calculated from the reference start date, and will be used to show start/stop day of assessments and events.

Reference start date is defined as the day of the first dose of study medication (Day 1 is the day of the first dose of study medication), and will appear in every listing where an assessment date or event date appears.

- If the date of the event is on or after the reference date then:

Document: L:\BIOS\Boehringer_Ingelheim_Pharmaceuticals\BI730357\1407-0037_MZA56588\Biostatistics\Documentation\SAP

Author: [REDACTED] Version Number: Final V2.0
Version Date: 23JUL2020

Template No: CS_TP_BS016 – Revision 5
Effective Date: 01Apr2018

Reference: CS_WI_BS005

Study Day = (date of event – reference date) + 1.

- If the date of the event is prior to the reference date then:
Study Day = (date of event – reference date).

In the situation where the event date is partial or missing, Study Day, and any corresponding durations will appear partial or missing in the listings.

6.5. BASELINE

Unless otherwise specified, baseline is defined as the last scheduled non-missing measurement taken prior to dosing and will generally correspond to Day -1 or Day 1, predose for safety assessments. However, if a subject is missing the planned baseline collection, the previous non-missing scheduled evaluation will become the baseline value. In the case where the last scheduled non-missing measurement (except for AEs and concomitant medications [CMs]) and the date and/or time of study drug coincide, that measurement will be considered as collected prior to study drug administration.

Baseline for photosensitivity assessments will be the assessment collected on Day -2 (Conditions 1 and 2) or Day -1 (Condition 3) (see Section 15.1 for the definitions of baseline for photosensitivity assessment)

6.6. RETESTS, UNSCHEDULED VISITS AND EARLY TERMINATION DATA

Unscheduled measurements will not be included in summary statistics, but will contribute to the best/worst case value where required (e.g. shift tables) and assessment of clinical outliers. Early termination results will be recorded as such, and included with the end-of-treatment (EOT) summaries.

In the case of a retest of a scheduled assessment, the earliest available measurement for that scheduled time (i.e. the original assessment) will be used for summaries unless flagged as invalid.

Listings will include all scheduled, unscheduled, retest and early discontinuation data.

6.7. COMMON CALCULATIONS

For quantitative measurements, change from baseline will be calculated as:

- Value after baseline – Baseline Value

6.8. SOFTWARE VERSIONS

All derivations, statistical analyses, summaries and listings will be generated using SAS version 9.4 or

Document: L:\BIOS\Boehringer_Ingelheim_Pharmaceuticals\BI730357\1407-0037_MZA56588\Biostatistics\Documentation\SAP
Author: [REDACTED] Version Number: Final V2.0
Version Date: 23JUL2020

Template No: CS_TP_BS016 – Revision 5
Effective Date: 01Apr2018

Reference: CS_WI_BS005

higher (SAS Institute, Inc., Cary, North Carolina). Non-compartmental pharmacokinetic parameter calculations will be performed using Phoenix® WinNonLin 64 Build 8.1.0.3530.

7. STATISTICAL CONSIDERATIONS

7.1. MISSING DATA

Missing safety data will not be imputed.

8. OUTPUT PRESENTATIONS

APPENDIX 1 shows conventions for presentation of data in outputs.

The templates provided with this TSAP describe the presentations for this study and therefore the format and content of the summary tables, figures and listings to be provided by [REDACTED] Biostatistics.

9. DISPOSITION AND WITHDRAWALS

Subject disposition and withdrawals will be tabulated by treatment part/treatment for the enrolled set by summarizing the number (percent) of subjects:

- Enrolled
- Failed screening
- Randomized
- Treated
- Completed treatment
- Discontinued treatment prematurely, and the reason for early discontinuation
- Completed study
- Discontinued study prematurely, and the reason for early discontinuation.

The denominator for calculating percentages will be the number of subjects in the respective treatment group.

A listing of subject disposition data will be provided. In a separate listing, the inclusion/exclusion of subjects in the different analysis sets will be presented.

Listings of study eligibility, treatment randomization, and study treatment administration will be

Document: L:\BIOS\Boehringer_Ingelheim_Pharmaceuticals\BI730357\1407-0037_MZA56588\Biostatistics\Documentation\SAP

Author: [REDACTED] Version Number: Final V2.0
Version Date: 23JUL2020

Template No: CS_TP_BS016 – Revision 5
Effective Date: 01Apr2018

Reference: CS_WI_BS005

provided.

10. DEMOGRAPHIC AND OTHER BASELINE CHARACTERISTICS

The following demographic and baseline characteristics will be tabulated by treatment and overall for the treated set:

- Age (years)
- Sex
- Childbearing status
- Race
- Ethnicity
- Height (cm)
- Weight (kg)
- Body mass index (BMI) (kg/m²)
- Fitzpatrick skin type.

Descriptive statistics (n, mean, SD, median, IQR, minimum, and maximum) will be presented for continuous variables. Frequency counts and percentages will be presented for categorical variables. No statistical testing will be carried out for demographic or other baseline characteristics.

Individual subject demographics and baseline characteristics will be presented in listings.

10.1. DERIVATIONS

- BMI (kg/m²) = weight (kg)/ height (m)²
- Age (years) = Integer value of [(Date of informed consent – date of birth + 1)/365.25]

11. PROTOCOL DEVIATIONS

11.1. DEVIATIONS RELATED TO STUDY CONDUCT

A protocol deviation is any noncompliance with the clinical trial protocol, good clinical practice (GCP), or Manual of Procedure requirements. The noncompliance may be either on the part of the subject, the site principal investigator, or the study site staff. Protocol deviations will be listed including a

Document: L:\BIOS\Boehringer_Ingelheim_Pharmaceuticals\BI730357\1407-0037_MZA56588\Biostatistics\Documentation\SAP

Author: [REDACTED] Version Number: Final V2.0
Version Date: 23JUL2020

Template No: CS_TP_BS016 – Revision 5
Effective Date: 01Apr2018

Reference: CS_WI_BS005

classification of minor, major or critical as determined by clinical staff. Whether a protocol deviation is relevant for the statistical analysis will be decided no later than in the final blinded report planning meeting.

The reasons for exclusion of single data may include (but are not limited to):

- Incorrect trial medication taken
- Important violation of treatment compliance
- Use of restricted medications
- Important violation of inclusion/exclusion criteria
 - Inclusion Criteria 1 - Healthy male and female subjects according to the assessment of the Investigator, based on a complete medical history, physical examination (including dermatological skin type assessment), vital signs (blood pressure, pulse rate), 12-lead ECG, and clinical laboratory tests
 - Inclusion Criteria 4 - Fitzpatrick skin type I, II, or III (I: always burns easily, never tans; II: always burns easily, tans minimally; and III: burns moderately, tans gradually)
 - Inclusion Criteria 5 - No ultraviolet exposure of the test areas 4 weeks prior to baseline photo testing
 - Inclusion Criteria 6 - Normal skin response during preliminary photo testing
 - Exclusion Criteria 6 - Active skin disorders on the back where photosensitivity testing will be performed
 - Exclusion Criteria 7 - Subjects who must or wish to continue the intake of restricted medications or any drug considered likely to interfere with the safe conduct of the trial
 - Exclusion Criteria 12 - -History of hypersensitivity to ciprofloxacin, any member of the quinolone class of antibacterials
 - Exclusion Criteria 22 - -Unwillingness to adhere to the rules of UV-light protection as described in section 4.2.2 of the protocol

Document: L:\BIOS\Boehringer_Ingelheim_Pharmaceuticals\BI730357\1407-0037_MZA56588\Biostatistics\Documentation\SAP

Author: [REDACTED] Version Number: Final V2.0
Version Date: 23JUL2020

Template No: CS_TP_BS016 – Revision 5
Effective Date: 01Apr2018

Reference: CS_WI_BS005

12. MEDICAL HISTORY AND PREVIOUS SURGICAL PROCEDURES

Medical History and previous surgical procedures coded using Medical Dictionary for Regulatory Activities (MedDRA) will be listed for the treated set.

13. MEDICATIONS

Medication usage will be coded using the WHO Drug Dictionary Global (Enhanced w/WHO Herbal Dictionary) B3 format. No Anatomical Therapeutic Chemical (ATC) class coding will be performed.

- 'Prior' medications are medications which started and stopped prior to the first dose of study medication.
- 'Concomitant' medications are medications which were taken during the treatment period, or specifically:
 - started on or after the first dose of study medication or
 - started prior to the first dose of study medication and were continued after the first dose of study medication
- 'Post' medications are medications which started after following the last dose of study medication.

See APPENDIX 2 for handling of partial dates for medications, in the case where it is not possible to define a medication as prior, concomitant, or post treatment, the medication will be classified by the worst case; i.e. concomitant.

All medications will be displayed in a listing, with an additional flag to state if the medication is a 'Prior', 'Concomitant' or 'Post' medication will be provided for the treated set.

14. STUDY MEDICATION EXPOSURE

In 400 mg QD dose group, BI 730357 and matching placebo will be administered QD over 8 days from

Document: L:\BIOS\Boehringer_Ingelheim_Pharmaceuticals\BI730357\1407-0037_MZA56588\Biostatistics\Documentation\SAP

Author: [REDACTED] Version Number: Final V2.0
Version Date: 23JUL2020

Template No: CS_TP_BS016 – Revision 5
Effective Date: 01Apr2018

Reference: CS_WI_BS005

Day 1 (total of 8 doses) in double-blind manner and ciprofloxacin will be administered BID over 5 days from Day 3 with a single dose on Day 8 (total of 11 doses) in an open-label manner. In 300 mg BID dose group, BI 730357 and matching placebo will be administered BID over 7 days from Day 1 with a single dose on Day 8 (total of 15 doses) in double-blind manner. Exposure to study medication as the number of doses administered will be presented by treatment for the treated set.

Study medication administration data will be provided in a data listing.

15. ANALYSIS OF PHOTOSENSITIVITY

For the assessment of photosensitivity, statistical analyses described below will be performed separately for the 400 mg QD dose group (randomized to 400 mg QD BI 730357 or placebo QD) and 300 mg BID dose group (randomized to 300 mg BID BI 730357 or placebo BID). The same ciprofloxacin group will be used as a positive control group in both analyses.

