4.1.2 Selection of doses in the trial and dose modifications

The dose of 400 mg BI 730357 QD or 300 mg BID for this trial are selected on the basis of the PK and safety data obtained in the SRD and MRD trials 1407.0001 and 1407-0002, preliminary PK and safety data obtained in patients with plaque psoriasis in the ongoing 1407.30 study, combined with the preclinical data (see section 1.1), are intended to cover the highest therapeutic dose range (including safety margin) chosen for the future clinical development of BI 730357 in diverse indications.

In the SRD trial, single dose levels up to 800 mg and in the MRD trial, multiple dose levels up to 400 mg were well tolerated in healthy volunteers, and doses up to 200mg were well tolerated in plaque psoriasis patients.

Blinded photosafety data will be evaluated by the independent Investigator and BI medical team after completion of the 400 mg BI 730357 or placebo QD treatment.

If no photo-safety concerns have been observed in the Treatment A group,300 mg BI 730357 or placebo BID will be conducted.

The Ciprofloxacin dose selected in this trial reflects the standard clinical dose with acceptable safety profile. Ciprofloxacin was chosen as the positive control based on its property as mild photosensitizer (R 19-2246, R 19-3127).

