4.1.3 Method of assigning subjects to treatment groups

After the assessment of all in- and exclusion criteria, each eligible subject will be first randomly allocated to part A 400 mg QD or part B in a 3 : 1 ratio, where Part A is initially set of patients who will either receive BI 730357 400mg QD or placebo.

Randomization list for this first step randomization process will be provided by BI to the dedicated staff.

c27983101-03 Clinical Trial Protocol Page 40 of 79

Proprietary confidential information © 2020 Boehringer Ingelheim International GmbH or one or more of its affiliated companies

Consequently, subjects allocated to the treatment Part A will be randomised according to a randomisation plan in a 3:1 ratio following the double blind design, which reflects the ratio of subjects receiving BI 730357 to placebo on Day 1.

Additionally, 12 subjects allocated to the treatment Part B will be assigned to receive Ciprofloxacin treatment.

A second set of 36 patients will be enrolled to either receive BI 730357 300mg BID or placebo. These patients will be randomized using the same double blind design and procedures as described for Part A above (for BI 730357 400mg QD or placebo) and randomized in a 3:1 ratio to BI 730357 300mg BID or placebo. Randomization list for this set of patients will also be provided by BI to the dedicated staff.

The appropriate medication number will be assigned and documented in the CRF.

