7.2.7 Interim Analyses

No statistical interim analysis is planned. However, after completion of the 400mg dose group the independent Investigator and BI medical representatives will review blinded photosafety data of treatment A group to determine the acceptability of photosafety. After the team review of these data, it may be recommended, or in case of unfavourable results - to test the higher dose of 300mg BID for treatment A. In addition, a preliminary blinded PK analysis will be performed to estimate the PK exposure.

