7.4 RANDOMISATION

The first set of subjects will be first randomised to the Treatment A (BI 400 mg QD/placebo) or Treatment B group in a 3:1 ratio. The random list will be provided by BI to the dedicated study staff.

Subjects allocated to the treatment group A will be randomised in a 3:1 ratio in a double blind manner, which reflects the ratio of subjects receiving active drug to placebo.

Subjects allocated to treatment B group will receive ciprofloxacin.

In order to investigate a second BI730357 dose of 300 mg BID, a second set of subjects be randomised in a 3:1 ratio in the same double blind manner described for Treatment A above, which reflects the ratio of subjects receiving active drug to placebo.

c27983101-03 Clinical Trial Protocol Page 67 of 79

Proprietary confidential information © 2020 Boehringer Ingelheim International GmbH or one or more of its affiliated companies

BI will arrange for the randomisation as well as packaging and labelling of trial medication for treatment A. The randomisation list will be generated using a validated system, which involves a pseudo-random number generator so that the resulting treatment will be both reproducible and non-predictable. The block size will be documented in the Clinical Trial Report. Access to the codes will be controlled and documented.

More details can be found in section 4.1.5.

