3. STUDY DESIGN

3.1. GENERAL DESCRIPTION

The trial will be performed as partially-blind, randomized, parallel group, placebo and active comparator controlled Phase I clinical trial in healthy male and female subjects aged ≥ 18 to ≤ 55 years. The subjects

Document: L:\BIOS\Boehringer_Ingelheim_Pharmaceuticals\BI730357\1407-0037_MZA56588\Biostatistics\Documentation\SAP

Author: [REDACTED] Version Number: Final V2.0
Version Date: 23JUL2020

Template No: CS_TP_BS016 – Revision 5
Effective Date: 01Apr2018

Reference: CS_WI_BS005

will be randomized to one of the two treatments parts (Treatment Part A [Treatment A] or Treatment Part B [Treatment B]) in a 3:1 (A:B) manner first and then Treatment Part A will be conducted according to a randomized, double-blind, placebo-controlled design to assess the photosensitivity potential, safety and tolerability, and pharmacokinetics of multiple doses of BI 730357. In Treatment A, subjects enrolled under the original protocol Version 1.0 will be randomized in a 3:1 manner to receive 400 mg QD of BI 730357 or placebo and subjects enrolled under the protocol Version 3.0 will be randomized in a 3:1 manner to receive 300 mg BID of BI 730357 or placebo.

Treatment Part B will be conducted according to an open-label, observer-blinded design to assess the photosensitivity potential of ciprofloxacin (a mild photosensitizer) as a positive control.

In total, approximately 84 healthy male and female subjects (36 subjects in Treatment A for 400 mg QD; 36 subjects in Treatment A for 300 mg BID; 12 subjects in Treatment B) are planned to be randomized in this trial to allow for at least 74 completed subjects.

Treatment A:

Subjects enrolled under Protocol Version 1.0 will receive 400 mg of BI 730357 or placebo once daily over 8 days in order to reach pharmacokinetic steady state. Similarly, subjects enrolled under Protocol Version 3.0 will receive 300 mg of BI 730357 or placebo twice daily 12 hours apart over 7 days with a single dose on Day 8 in order to reach pharmacokinetic steady state. Photosensitivity assessments will occur at baseline and following the last dose of either BI 730357 or placebo.

Treatment B:

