The alternative hypothesis will be that the means are not equal:

Alternative hypothesis H_a : $\mu_{\text{BI/pbo}} - \mu_{\text{cipro}} \neq 0$

A significant finding of increased photosensitivity of ciprofloxacin compared to BI 730357 400 mg QD and to placebo QD at the $p<0.05$ level will be supportive in concluding that the trial was appropriately designed to test the photosensitivity of BI 730357 400 mg QD.

15.3.2. 300 MG BID Dose Cohort

For comparisons of BI 730357 300 mg BID vs placebo BID, BI 730357 300 mg BID vs ciprofloxacin, and placebo BID vs ciprofloxacin, null and alternative hypotheses will be identical to the respective null and alternative hypotheses described above for the 400 mg QD dose cohort.

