15.4. PRIMARY ENDPOINT ANALYSIS OF PHOTOSENSITIVITY INDEX

400 mg QD Dose Cohort:

The primary analysis will be based on FAS for both conditions 1 and 2 at the 24 hour assessment.

Least squares (LS) mean for the difference between BI 730357 400 mg QD and placebo QD along with the corresponding 2-sided 90% CI will be obtained from the MMRM described in Section 15.2 above.

Absence of photosensitivity between BI 730357 400 mg QD and placebo QD will be concluded if the 2-sided 90% CI is fully contained within the acceptance range (-0.4, 0.4).

A significant finding of increased photosensitivity of ciprofloxacin compared to BI 730357 400 mg QD and to placebo QD at the $p<0.05$ level will be supportive in concluding that the trial was appropriately designed to test the photosensitivity of BI 730357 400 mg QD.

Document: L:\BIOS\Boehringer_Ingelheim_Pharmaceuticals\BI730357\1407-0037_MZA56588\Biostatistics\Documentation\SAP

Author: [REDACTED] Version Number: Final V2.0
Version Date: 23JUL2020

Template No: CS_TP_BS016 – Revision 5
Effective Date: 01Apr2018

Reference: CS_WI_BS005

Additionally, descriptive statistics by treatment will be provided for the primary endpoints.

For Conditions 1 and 2, figures of LS mean PI (+/- standard error [SE]) versus time points will be provided.

300 mg BID Dose Cohort:

The primary endpoint analysis of PI for the 300 mg BID dose cohort will be identical to that described above for the 400 mg QD dose cohort. Comparisons of BI 730357 300 mg BID vs placebo BID, BI 730357 300 mg BID vs ciprofloxacin, and placebo BID vs ciprofloxacin will be performed.

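### One covariance across all arms gives wrong error bars under the protocol's own SDs (conservative for BI 730357 vs placebo); separately, the reused ciprofloxacin group cannot show assay sensitivity for 300 mg BID

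*SAP*

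**What the plan says.** **Model.** For each dose cohort and irradiation condition, SAP 15.2 specifies one repeated-measures model with treatment (BI 730357 and placebo of that cohort, plus ciprofloxacin), time and their interaction. The text and the example SAS code ask for one unstructured covariance matrix, and the code has no `GROUP=` option. The written equation has a random subject effect and independent errors instead, again with the same variances in every arm. Under SAP 15.4 the 90% CI for BI 730357 minus placebo at 24 h must lie within ±0.4. Ciprofloxacin is tested against BI 730357 and placebo at p<0.05. A significant result is taken as support for the adequacy of the design (protocol 7.1; SAP 15.3.1 and 15.4).

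**Planning values.** Protocol 7.5 uses SD 0.15 for BI 730357 and placebo and 0.600 for ciprofloxacin, and powers the ciprofloxacin comparisons with a Satterthwaite t-test.

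**Source of the ciprofloxacin group.** Under protocol 7.4 the first subjects "will be first randomised to the Treatment A (BI 400 mg QD/placebo) or Treatment B group in a 3:1 ratio". Protocol 4.1.3 continues: "A second set of 36 patients will be enrolled to either receive BI 730357 300mg BID or placebo". Protocol 7.2.7 places a review in between: "after completion of the 400mg dose group the independent Investigator and BI medical representatives will review blinded photosafety data". SAP 3.1 confirms that "subjects enrolled under the protocol Version 3.0 will be randomized in a 3:1 manner to receive 300 mg BID of BI 730357 or placebo". SAP 15 then states: "The same ciprofloxacin group will be used as a positive control group in both analyses". For BID, SAP 15.3.2 says that the "null and alternative hypotheses will be identical to the respective null and alternative hypotheses described above for the 400 mg QD dose cohort", and SAP 15.4 says: "The primary endpoint analysis of PI for the 300 mg BID dose cohort will be identical to that described above". Both sections list BI 730357 BID and placebo BID against ciprofloxacin.

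**The concern.** The main issue is variance. If ciprofloxacin is four times as variable as the other arms, a shared covariance averages unlike variances. The result is too large for BI 730357 minus placebo, so the interval that decides equivalence is not a 90% interval. It is too small for the ciprofloxacin contrasts that are meant to support the assay. This affects both cohorts, including the concurrently randomised QD set.

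The smaller issue concerns 300 mg BID only. Absence of photosensitivity is an equivalence claim, and an insensitive assay favours such a claim. A positive control guards against this only if it is read in the same sessions. For BID it is not, and neither document says what follows from that.

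**Working it through.** **Inputs.** Arm sizes are 27 BI 730357 and 9 placebo per cohort (protocol 3.2), and 12 ciprofloxacin. SDs are 0.15, 0.15 and 0.60, and the ciprofloxacin difference is 0.6 (protocol 7.5). The margin is 0.4 (protocol 7.1). The calculation takes one timepoint with complete data. In that case the unstructured model reduces at 24 h to one variance pooled over three arms, with 26 + 8 + 11 = 45 df.

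**1. The protocol's figures.** Satterthwaite power is 87.8% for 12 vs 27 (df 11.6; stated 87%) and 86.7% for 12 vs 9 (df 12.8; stated 86%). Equivalence power with SD 0.15 exceeds 99.99% (stated 99%). The stated figures reproduce, but for tests that the SAP model does not perform.

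**2. Pooled SD.** √[(34 × 0.15² + 11 × 0.60²)/45] = √(4.725/45) = 0.324.

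**3. Standard errors.**

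| Contrast | Under the SAP model | True |
|---|---|---|
| BI 730357 − placebo | 0.324 × √(1/27 + 1/9) = 0.125 | 0.15 × √(1/27 + 1/9) = 0.058 |
| Ciprofloxacin − BI 730357 | 0.324 × √(1/12 + 1/27) = 0.112 | √(0.36/12 + 0.0225/27) = 0.176 |
| Ciprofloxacin − placebo | 0.324 × √(1/12 + 1/9) = 0.143 | √(0.36/12 + 0.0225/9) = 0.180 |

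The 90% half-width for BI 730357 − placebo is 1.679 × 0.125 = 0.21 under the SAP model. It is 0.098 from the two arms alone (34 df). Simulated means are 0.206 and 0.097, with coverage 99.8% and 90.0%.

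**4. Probability of concluding equivalence (simulated).**

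| True difference | SAP model | Without ciprofloxacin |
|---|---|---|
| 0 | 99.4% to 99.5% | 100% |
| 0.2 | 47% | 96% |
| 0.3 | 6% | 52% |
| 0.4 | 0.1% | 5.0% |

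**5. Sensitivity to the ciprofloxacin SD** (0.30 and 0.15 are assumptions). The last two columns give the true two-sided error of the nominal 5% test when all means are equal.

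| Ciprofloxacin SD | 90% CI coverage | vs placebo | vs BI 730357 |
|---|---|---|---|
| 0.60 | 99.8% | 13% | 22% |
| 0.30 | 96.5% | 9% | 14% |
| 0.15 | 90.0% | 5% | 5% |

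At SD 0.60 the Satterthwaite test holds 5.1% for both contrasts. With the SDs of the cited study (0.12 and 0.55, using 0.12 for BI 730357 too), coverage is 99.9%.

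**6. Does the covariance form matter?** A five-timepoint simulation (assumed within-subject correlation 0.6, complete data) gave coverage of 99.8% for the unstructured matrix and 99.9% for the random-subject equation. The half-width was 0.206 for both. Without ciprofloxacin it was 89.7% and 0.097. The problem is the same whichever form is fitted.

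**7. The BID comparisons.** The 3:1 split between Parts A and B fits 36:12; 72:12 would be 6:1. The general wording in protocol 3.1 and 3.2 and SAP 3.1 therefore creates no ciprofloxacin arm for BID. Suppose BID-period readings could detect nothing. Placebo BID would still sit near 1.0 and the earlier ciprofloxacin readings near 1.6, so a Satterthwaite test would still pass about 87% of the time, as it would with fully sensitive readings. The BID contrasts also share the ciprofloxacin data with the QD ones: their correlation is 0.030/(0.030 + 0.0025) = 0.92 against placebo and 0.030/(0.030 + 0.00083) = 0.97 against BI 730357. They largely repeat the QD check.

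**The case against.** **On the covariance.**
- The error on the deciding contrast is conservative and costs almost nothing at the planned difference of 0. This stands. A reader might infer that the SAP model makes a false finding of no photosensitivity more likely; the figures show the opposite.
- The 13% and 22% error rates need a ciprofloxacin group with no mean effect but SD still 0.60. If the extra spread comes from the response itself, an assay that detects nothing would give an SD nearer 0.15 and no distortion. This stands, so a flat statement that the ciprofloxacin tests are too liberal is not supported.
- The cited SDs are taken over all PI measurements and may not describe 24 h under one condition. This stands as a condition, but 0.60 and 0.15 are the plan's own values.
- The SAS code is offered only as an example. That does not help, since the text and the equation also share variances across arms.

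**On the reuse.** SAP 15 discloses it, and SAP 14 places ciprofloxacin dosing with the 400 mg QD group. The decision rests on BI 730357 versus placebo alone, and the ciprofloxacin result is only supportive. The SAP's sentence on design adequacy names 400 mg QD and reaches BID only through the word identical and the trial-level wording of protocol 7.1. There is one site, few evaluators, blinded assessment, and a PI relative to each subject's own baseline. All this stands and makes it the lesser point. These safeguards limit drift; they do not demonstrate sensitivity. A reader might infer that the reuse biases the BID equivalence result. It does not, because that contrast is randomised and concurrent.

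**Conclusion.** The main point holds, conditional on the protocol 7.5 SDs applying at 24 h. As written, the nominal 90% CI for BI 730357 minus placebo is about twice as wide as it should be. The practical cost is lost power away from a difference of 0, not a false claim of equivalence. The ciprofloxacin standard errors are too small by about a third against BI 730357 (0.112/0.176 = 0.64) and a fifth against placebo (0.143/0.180 = 0.79). Whether this inflates type I error depends on the ciprofloxacin SD when there is no effect, with a range of 5% to 22%.

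The smaller point also holds. For 300 mg BID the ciprofloxacin comparisons are non-concurrent and non-randomised, and assay sensitivity is carried over from the QD set by assumption. This limits what may be claimed for BID and leaves its BI 730357 versus placebo estimate untouched. The change should be made; neither point invalidates the trial.

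**What to change.** **Covariance (both cohorts, both conditions).** Estimate BI 730357 minus placebo from the same model without the ciprofloxacin arm. Test ciprofloxacin against BI 730357 and placebo at each timepoint with a Satterthwaite test, matching protocol 7.5. A `GROUP=` covariance for ciprofloxacin is an option only with a simpler structure pre-stated as fallback, because an unstructured 5×5 matrix (15 parameters) would rest on 12 subjects. SAP 15.5 borrows the same model, so its wording should follow.

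**BID comparisons.** In SAP 15, 15.3.2 and 15.4, label them non-concurrent, non-randomised and descriptive. Do not apply the p<0.05 reading on design adequacy to BID. State that assay sensitivity rests on ciprofloxacin versus placebo QD and is carried over by assumption. Placebo BID minus placebo QD with its CI may be added as a drift check. It is coarse (9 vs 9, SD 0.15, 16 df: 90% half-width about 0.12) and cannot show sensitivity.

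Record both in SAP 3.3, as changes from protocol 7.2.2 and 7.1 respectively, before unblinding.

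**Cost.** SAP wording, refits of four PI models (2 cohorts × 2 conditions), the separate ciprofloxacin tests and one optional contrast; no new subjects or procedures. Downsides: both ciprofloxacin tests are significant in about 85% of trials instead of 95%. Equivalence becomes easier to conclude than under the written model, with error at a true difference of 0.4 rising from 0.1% to the nominal 5%. The supporting claim for BID is weaker.
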